6.2 Exclusion Criteria

The patient may not enter the trial if ANY of the following apply:

- 6.2.1 Has taken nabiximols, cannabis, or a cannabis-derived product for medicinal or recreational purposes in the 30 days prior to Visit 1 and unable to abstain for the duration of the study.
- 6.2.2 Did not tolerate or did not respond adequately to treatment with nabiximols or another cannabis-based medication if exposed at any time before the 30-day period prior to Visit 1.
- 6.2.3 Any concomitant disease or disorder that has spasticity-like symptoms or that may influence the patient's level of spasticity.
- 6.2.4 Medical history suggests that relapse/remission is likely to occur during the trial, which, in the opinion of the investigator, is expected to influence the patient's spasticity.
- 6.2.5 Has had a relapse of MS within the 60 days prior to Visit 1.
- 6.2.6 Currently using botulinum toxin injection for the relief of spasticity (within 6 months of Visit 1) and is unwilling to abstain for the duration of the trial.
- 6.2.7 Currently taking antipsychotic medication.

- 6.2.8 Currently taking benzodiazepines unless doses and dosing regimen have been stable for at least 30 days prior to Visit 1.
- 6.2.9 Clinically suspected to have a contracture in one of the muscle groups of the lower limbs, preventing assessment with the MAS.
- 6.2.10 Has any known or suspected hypersensitivity to cannabinoids or any of the excipients of the IMP.
- 6.2.11 Has experienced myocardial infarction or clinically significant cardiac dysfunction within the last 12 months prior to Visit 1 or has a cardiac disorder that, in the opinion of the investigator, would put the patient at risk of a clinically significant arrhythmia or myocardial infarction.
- 6.2.12 Has a diastolic blood pressure of < 50 mmHg or > 105 mmHg or systolic blood pressure < 90 mmHg or > 150 mmHg (when measured in a sitting position at rest for 5 minutes) or a postural drop in the systolic blood pressure of > 20 mmHg at Visit 1 or Visit 2. All measurements will be performed singly and can be repeated once, if any are outside the reference range but not considered clinically significant.
- 6.2.13 Has clinically significant impaired renal function at Visit 1, as evidenced by an estimated creatinine clearance lower than 50 mL/min. All measurements will be performed singly and can be repeated once, if any are outside the reference range but not considered clinically significant.
- 6.2.14 Has moderately impaired hepatic function at Visit 1, defined as serum alanine aminotransferase (ALT) or aspartate aminotransferase (AST) > 2 × upper limit of normal (ULN). All measurements will be performed singly and can be repeated once, if any are outside the reference range but not considered clinically significant.
- 6.2.15 Male and fertile (i.e., after puberty unless permanently sterile by bilateral orchiectomy) unless willing to ensure that he uses male contraception (condom or vasectomy) or remains sexually abstinent during the trial and for 3 months thereafter.
- 6.2.16 Female and of childbearing potential (i.e., following menarche and until becoming postmenopausal for ≥ 12 consecutive months unless permanently sterile by hysterectomy, bilateral salpingectomy, or bilateral oophorectomy) unless willing to ensure that she uses a highly effective method of birth control (e.g., intrauterine device/hormone-releasing system, bilateral tubal

occlusion, vasectomized partner, or sexual abstinence) during the trial and for 3 months thereafter. Patients using combined hormonal methods or a progestogen-only pill or injection or implant should use an additional barrier method such as a condom or diaphragm during the trial and for 3 months thereafter (see [Section 9.2.2](#)).

- 6.2.17 Female and pregnant (positive pregnancy test at Visit 1 or Visit 2), lactating, or planning pregnancy during the course of the trial or within 3 months thereafter.
- 6.2.18 Has received an IMP within the 30 days prior to Visit 1.
- 6.2.19 Has any other clinically significant disease or disorder (including seizure disorder) that, in the opinion of the investigator, may put the patient, other patients, or site staff at risk because of participation in the trial, may influence the interpretation of trial results, or may affect the patient's ability to take part in the trial.
- 6.2.20 Has any abnormalities identified following a physical examination, clinical laboratory, serology, or other applicable screening procedures that, in the opinion of the investigator, would jeopardize the safety of the patient or the conduct of the study if he or she took part in the trial.
- 6.2.21 Has any history of suicidal behavior in the 5 years prior to Visit 1 or a score of 3, 4, or 5 on the C-SSRS in the month prior to Visit 1.
- 6.2.22 Has donated blood during the 3 months prior to Visit 1 and is unwilling to abstain from donation of blood during the trial.
- 6.2.23 Has been previously randomized into this trial.
- 6.2.24 Has any known or suspected history of alcohol or substance abuse (including opiate abuse) or dependence within 1 year prior to Visit 1.
- 6.2.25 Currently using an illicit drug or current nonprescribed use of any prescription drug.
- 6.2.26 Has a history of psychiatric or neurologic disorder that, in the opinion of the investigator, may interfere with trial participation, data interpretation, or conduct of trial procedures.
- 6.2.27 Has a history of severe psychiatric disorder that may be exacerbated by the use of a cannabinoid-containing product.

- 6.2.28 Has any planned clinical interventions or intends to change any or all medications that may have an effect on spasticity or MS during the trial.
- 6.2.29 Currently taking drugs that are solely metabolized by UGT1A9 and UGT2B7 (see [Appendix 4](#)).
- 6.2.30 Currently taking strong CYP3A4 inducers (e.g., rifampicin, carbamazepine, phenytoin, phenobarbital, St John's Wort).

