9.1.2.1 Visit 2 (Day 1)

Patients will return to the site in the morning of Day 1 when eligibility will be confirmed and patients will be randomized.

The following assessments/procedures will be performed on Day 1 predose:

- Eligibility check
- Randomization ([Section 7.2](#))
- Concomitant medications review
- AE review
- Examination of oral mucosa
- Body weight measurement

- Vital signs measurement
- Urine drug screen (including THC)
- Urine pregnancy test (if appropriate)
- PK blood sampling for IMP ([Section 9.2.12.1](#))
- MAS assessment
- T25FW test ([Section 9.2.15.4](#))
- C-SSRS assessment
- IMP dosing training ([Section 9.2.14.3](#))
- IMP dispensing

Following predose assessments and after IMP dosing training and dispensing, site staff will observe dosing by the patient and verify that IMP was correctly administered.

Patients will administer a single dose of IMP with a standardized snack containing at least 300 kcal (of which approximately 30 kcal is composed of fat) at the trial site under the supervision of site staff.

The following assessments/procedures will be performed 2 to 4 hours postdose:

- MAS assessment (3 hours \pm 15 minutes postdose)
- AE review
- Vital signs measurement
- PK blood sampling for IMP ([Section 9.2.12.1](#))

The patient will be provided dosing instructions and advised to contact the investigational site when in doubt about changes in the daily dose of IMP. The patient will be instructed to record IMP doses administered in the patient electronic diary.

The exact time of PK blood sampling and the time of the patient's snacks and meals should be recorded.

Following Visit 2, patients will titrate their daily dose of IMP for approximately 14 days until they achieve an optimized dose with an approximately 15-minute interval between sprays; patients should divide doses greater than 1 spray/day into a morning dose and an evening dose. Administration of the morning and evening doses of IMP should be maintained around the same time each day in a consistent manner in relation to food consumption, i.e., within 30 minutes after starting a snack or meal.

Patients should be reminded to record their 11-point NRS spasticity score, spasm count, and use of antispasticity medications in the electronic diary once daily, around the same time each day, preferably in the evening before retiring to sleep. In addition, on the day

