9.2.10 Vital Signs

As part of the screening procedures at Visit 1, vital signs (systolic and diastolic blood pressure and pulse rate) will first be measured after the patient assumed a supine position for 5 minutes. Vital signs will then be measured within 2 minutes of assuming a standing position in ambulatory patients only. At all subsequent time points, vital sign

measurements will be completed in a sitting position at rest for 5 minutes. Blood pressure should be recorded using the same arm throughout the trial, where possible.

Additional vital signs measurements may be taken during the trial if clinically indicated.

9.2.11 12-Lead Electrocardiogram

A 12-lead ECG will be performed after 5 minutes in a supine position. A physician must review the ECG (annotated, signed, and dated) and any abnormal findings considered to indicate significant medical history or AEs must be recorded appropriately on the eCRF. Additional ECG measurements can be taken at any time during the trial, if clinically indicated.

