12.7.4 Vital Signs

Vital signs will include sitting SBP and DBP and pulse rate which are planned to be measured at Day 1 H0, D1H3, Day 15 and D21 of each treatment period as well as during the screening and the FU visit.

Vital signs parameters will be summarized on the Safety Analysis Set as described below.

Observed and change from baseline value in vital signs measures at each scheduled timepoint (D1H3, Day 15, D21) will be summarized by treatment arm.

The number and percentage of patients with any clinically significant abnormal value and change in vital signs (as defined in Appendix 6) within each treatment period will be summarized by treatment arm within the Safety Analysis Set.

Observed and change from baseline (Screening) to FU will also be summarized by treatment sequence.

All vital signs data will be listed.

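### Exclusion 6.2.12 sets sitting blood-pressure limits and a postural-drop limit at Visit 1 or Visit 2, but Section 9.2.10 schedules no sitting reading at Visit 1 and no postural pair at Visit 2

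*Protocol*

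**What the plan says.** Protocol Section 6.2, criterion 6.2.12, has two parts. The first sets lower and upper limits for systolic pressure (90 and 150 mmHg) and diastolic pressure (50 and 105 mmHg), "when measured in a sitting position at rest for 5 minutes". The second excludes on posture: "or a postural drop in the systolic blood pressure of > 20 mmHg at Visit 1 or Visit 2". The synopsis repeats the criterion with the same limits, posture and visits.

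Protocol Section 9.2.10 governs how the readings are taken. At Visit 1, vital signs "will first be measured after the patient assumed a supine position for 5 minutes". Then: "Vital signs will then be measured within 2 minutes of assuming a standing position in ambulatory patients only". At all later time points, "measurements will be completed in a sitting position at rest for 5 minutes". It adds: "Additional vital signs measurements may be taken during the trial if clinically indicated".

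The procedure list for Visit 2 (Section 9.1.2.1) gives only "Vital signs measurement", with no posture. The Visit 1 list (Section 9.1.1) and the schedule in Appendix 1 with its footnotes also give no posture.

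SAP Section 12.7.4 states: "Vital signs will include sitting SBP and DBP and pulse rate". It lists screening and follow-up among the planned time points and plans a summary, by treatment sequence, of the change from a screening baseline to follow-up. SAP Section 12.2.3 defines the baseline orthostatic values as supine minus standing.

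**The concern.** The criterion and the measurement procedure name different postures at the two eligibility visits. A site following 9.2.10 exactly has no sitting value at Visit 1 to compare with the sitting limits. It has no pair of postures at Visit 2 from which to calculate a drop.

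This is a safety exclusion, and eligibility is formally rechecked before the first dose at Visit 2. Screening can last up to 28 days, so the only scheduled postural reading may be up to four weeks old on the day of dosing. In non-ambulatory patients there is none. What is at stake is whether the eligibility rule can be applied, and deviations from it judged, from the readings the protocol schedules. The same mismatch affects one vital-signs summary in the SAP.

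**Working it through.** The plan gives no figure to reproduce. The check sets the criterion beside the procedure.

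**Step 1: scheduled readings by visit (Section 9.2.10).** Visit 1: supine, then standing if ambulatory. Visit 2: sitting.

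**Step 2: what each part of 6.2.12 needs.** The limits need a sitting reading. The drop needs readings in two postures. 6.2.12 does not name the pair, but 9.2.10 (supine, then standing) and SAP 12.2.3 (supine minus standing) both point to the same one. A single sitting reading cannot yield a drop under any definition.

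**Step 3: cross the two.**

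| Part of 6.2.12 | Visit 1 | Visit 2 predose |
|---|---|---|
| Sitting limits | no scheduled reading | scheduled |
| Postural drop | scheduled, ambulatory patients only | no scheduled reading |

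With 2 parts × 2 visits = 4 checks, 2 have no scheduled reading in any patient. In ambulatory patients, each part has one scheduled reading before the first dose.

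**Step 4: does the count depend on how the visit phrase is read?**

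- If a finding at either visit excludes, and the phrase covers both parts, 2 of 4 checks lack a scheduled reading.
- If the phrase attaches only to the postural part, 1 of its 2 checks (Visit 2) lacks a reading, and no visit is stated for the sitting limits.
- If one check of each part at either visit is enough, no check is missing in ambulatory patients.

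The protocol's own usage favours the first reading. Exclusion 6.2.17 uses the same visit phrase for a positive pregnancy test, and pregnancy tests are scheduled at both visits. The neighbouring criteria 6.2.13 and 6.2.14 name Visit 1 alone, so naming two visits in 6.2.12 appears deliberate.

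**Step 5: non-ambulatory patients.** No criterion in Sections 6.1 or 6.2 requires ambulation, and the Appendix 1 footnote on the walk test provides for patients who cannot walk. They can therefore be enrolled. Section 9.2.10 gives them no standing reading at Visit 1, and Visit 2 is sitting only, so they have no scheduled postural reading. 6.2.12 says nothing about them.

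**Step 6: carry-over to the SAP.** Under 9.2.10 the screening values are supine or standing and the follow-up values (Visit 10) are sitting. The screening-to-follow-up change in SAP 12.7.4 would therefore subtract readings taken in different postures. The other changes from baseline in that section need not have this problem. The SAP's baseline definition for clinic-based safety endpoints (Section 10.2) is the last record before the first dose, which for sitting pressure is the Visit 2 predose value.

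**The case against.** The strongest defence is that the criterion joins the visits with "or". Read together with 9.2.10, each part then has one scheduled reading before the first dose: the drop at Visit 1 and the sitting limits at Visit 2. This reading is possible, and its factual core stands for ambulatory patients. It is still the weaker reading, given how 6.2.17 uses the same phrase, and it leaves non-ambulatory patients unaddressed.

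Second, 9.2.10 sets scheduled readings and does not forbid others, and 6.2.12 itself names the posture for the limits. A site could take a sitting reading at Visit 1. That stands against any claim that the checks cannot be made. It does not supply a scheduled check, because the extra readings are for clinical indication, and the single repeat that 6.2.12 allows is for out-of-range values.

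Third, limiting standing readings to ambulatory patients is a deliberate feasibility limit. That stands. The gap is only that 6.2.12 does not reflect it.

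Fourth, SAP 12.7.4 may suggest that sitting values at screening were intended. It does not override the protocol, so it adds a passage to reconcile.

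Fifth, there are other safeguards. Dosing starts with one supervised spray on site, vital signs and adverse events are reviewed 2 to 4 hours later, and exclusions 6.2.11, 6.2.19 and 6.2.20 leave room for investigator judgement. These limit the consequence but do not remove the inconsistency.

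**Conclusion.** The point holds as an internal inconsistency. On the more natural reading, 2 of the 4 visit-by-criterion checks in 6.2.12 have no scheduled reading under 9.2.10. Non-ambulatory patients have no scheduled postural reading, and one SAP summary would mix postures. The primary LLMT-6 analysis and the sample size are unaffected.

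The count assumes that a finding at either visit excludes and that the visit phrase covers both parts. Under the most lenient reading the count falls to zero in ambulatory patients, but the non-ambulatory gap and the SAP mismatch remain.

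A reader might infer more than the documents support:

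- That a postural drop on the dosing day cannot be detected. Additional readings are allowed when clinically indicated; what is absent is a scheduled one.
- That sites will apply sitting limits to supine values, skip the check, or judge eligibility differently from one another. The protocol expects about 20 sites, but nothing in the documents shows how they behave.
- That the non-ambulatory restriction is a further contradiction to add to the count. It is a stated limit, and the documents do not give the number of such patients, so it does not measure impact.

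**What to change.** 1. Reconcile the synopsis criterion, 6.2.12 and 9.2.10 so that the posture and visit named in the criterion match the posture and visit measured. Either the readings or the criterion can change; that is for the sponsor to decide. The wording should also make clear whether the visit phrase covers both parts and whether a finding at either visit excludes.
2. State in 6.2.12 how the postural part is handled in non-ambulatory patients.
3. Align SAP 12.7.4 with the protocol on screening posture, and make the change-to-follow-up summary compare like postures. One option is to use the sitting Visit 2 predose value, already collected, as baseline. That also agrees with the SAP's own definition of a safety baseline.

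The cost is amendment wording and a short SAP edit or, if readings are added instead, a few minutes with the same device and staff.

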7 PATIENT ENROLLMENT

Before patients may be entered into the trial, GW requires a copy of the relevant site's institutional review board (IRB) or independent ethics committee (IEC) written approval of the protocol, informed consent form (ICF), and other patient information material. Patients will be considered enrolled in the trial from the time of providing written informed consent. All patients must personally sign and date the consent form prior to any procedures being performed (refer to [Section 9.2.1](#) and [Section 15.2](#)).

7.1 Treatment Assignment

At the start of Visit 1, enrolled patients will be allocated a unique patient number in a sequential order by trial site. Following randomization, GW will provide all IMP in a packed and labeled state, and the IRT will identify the pack number to be dispensed to the patient at each relevant visit according to the treatment sequence assigned in the randomization schedule.

7.2 Randomization

The allocation of IMP to treatment number will be done according to a randomization schedule produced by an independent statistician. The randomization schedule will be held centrally on the IRT and not divulged to any other person involved in the trial until the database has been locked and unblinding authorized by the relevant GW personnel. For access to blinded treatment assignment, see [Section 8.6](#). If more than 6 patients withdraw from the trial, additional patients will be enrolled to have 46 completers.

8 TREATMENT PROCEDURES

8.1 Investigational Medicinal Product Dosage, Administration, and Schedule

The IMP will be presented as a pump oromucosal spray. Nabiximols oromucosal spray is a mixture of THC and CBD extracts derived from *Cannabis sativa* L. Each of the botanical extracts contains a cannabinoid as the major constituent (i.e., THC or CBD) and minor constituents, including other cannabinoid and non-cannabinoid plant components, such as terpenes, sterols, and triglycerides.

The use of placebo in the current trial is deemed necessary to determine the efficacy or safety of the current intervention(s), since the best proven intervention has already been tried/is being given as background treatment and has failed to/does not fully alleviate the patient's symptoms. Placebo to match nabiximols is presented as an oromucosal spray containing excipients, coloring, and flavoring, with no active ingredients.

For details regarding IMP formulations, see [Section 5](#).

8.1.1 Dose Administration

For all treatment sequences, IMP will be administered by the patient via a pump actuation of oromucosal spray. The IMP will be self-administered to the oral mucosa. Patients will receive IMP dosing training from site staff on Visit 2 (Day 1 predose). Patients will be advised to administer IMP at approximately the same time each day in a consistent manner in relation to food consumption. Morning and evening doses should be administered around the same time within 30 minutes after starting a snack or meal. Patients should divide doses greater than 1 spray/day into a morning dose and an evening dose. On the days of scheduled MAS assessments other than Visit 1 (i.e., Visits 2, 5, 6, and 9), patients will attend the trial site without having administered any IMP in the morning. On the days of MAS assessment, patients who are taking baclofen and/or tizanidine as part of their optimized antispasticity therapy should take their regular morning dose of either or both medication(s) at least 1 hour before the administration of IMP. Administration of the morning dose of IMP with a standardized snack containing at least 300 kcal (of which approximately 30 kcal is composed of fat) will occur at the trial site under the supervision of site staff.

Following the titration phase (see [Section 8.1.2](#)), IMP will be administered as 1 spray (100 µL per spray) with a target interval of approximately 1 minute, until the patient's

specific optimized dose has been administered. Patients should be advised to direct each spray at a different site on the oromucosal surface, changing the application site for each spray of the IMP. If lesions are observed or persistent soreness is reported, the IMP administration must be interrupted until complete resolution occurs. Events of this nature are to be recorded according to the adverse event (AE) procedures (see [Section 12](#)).

8.1.2 Dose Escalation and Dose Adjustments

Site staff will demonstrate proper dosing and then observe dosing by the patient at Visit 2 (Day 1) and verify that IMP was correctly administered. Patients will initiate IMP treatment as a single spray in the clinic in the morning of Visits 2 (Day 1) and 6 (Day 31) of each treatment period. Patients will gradually titrate their daily dose to the maximally acceptable dose, balancing efficacy and tolerability, or to a maximum number of 12 sprays/day. During the titration phase, there should be an approximately 15-minute interval between sprays. Patients may temporarily pause or slightly reduce the number of sprays upon the emergence of adverse events; the titration may be resumed when the AEs resolve. No further dose adjustments should take place after 14 days unless advised by the investigator. An example titration schedule is presented in [Table 8.1.2-1](#).

Patients should not take more than 12 sprays/day of IMP at any time during the trial. Patients should consult the dosing instructions provided and contact the investigational site when in doubt about changes in the daily dose of IMP at any time during the study.

Table 8.1.2-1 Example Titration Schedule

Day	Number of Sprays in the Morning	Number of Sprays in the Evening	Total Number of Sprays/Day
1	1	0	1
2	1	1	2
3	1	2	3
4	2	2	4
5	3	2	5
6	3	3	6
7	4	3	7
8	4	4	8
9	5	4	9
10	5	5	10
11	6	5	11
12	6	6	12
13	6	6	12
14	6	6	12

Patients should complete titration within approximately 14 days of their first dose of IMP in each treatment period and should continue at the same dose level achieved at the end of the titration phase (i.e., their daily optimized dose) ± 1 spray /day divided into a morning dose and an evening dose for the remainder of the treatment period. This guidance applies unless patients agree with the investigator to lower the dose of IMP to address poor tolerability. Once a stable daily dose has been reached, patients should gradually decrease the interval between sprays to a target interval of approximately 1 minute between sprays.

The total daily dose should be administered as a morning dose and an evening dose, which may be comprised of a different number of sprays during titration. During the period of stable dosing following titration, patients should attempt to achieve a balance in the number of sprays administered as part of the morning and evening doses of IMP.

